8.6. Warnings and Precautions

Special warnings or precautions for the study drug, derived from safety information collected by the sponsor or its designee, are presented in the Investigator's Brochure. Additional safety information collected between IB updates will be communicated in the form of Investigator Notifications (INs). Any important new safety information should be discussed with the subject during the study, as necessary. If new significant risks are identified, they will be added to the ICF.

8.7. Data Monitoring Committee

There will be no formal Data Monitoring Committee for this open-label study. For Part 1, the sponsor will conduct telephone conferences with investigators in order to review cohort-specific data, to review overall safety data from prior cohorts (if applicable), and to agree on dose

escalation, de-escalation, and cohort expansion decisions on a regular basis (ie, approximately weekly). For Part 2, safety and tolerability will be carefully monitored throughout the study by the sponsor on a regular basis (ie, approximately monthly).

8.8. Immune-Related Adverse Events

Adverse events of a potential immunologic etiology or irAEs may be defined as an AE consistent with an immune phenomenon associated with drug exposure after all other etiologies have been eliminated. Immune-related AEs may be expected based on the nature of INCAGN01876, its mechanism of action, and reported experience with other immunotherapies. Special attention should be paid to AEs that may be suggestive of potential irAEs. An irAE can occur shortly after the first dose or several months after the last dose of treatment. Guidance for the assessment, diagnosis, and management of irAEs is provided in [Section 5.4.7](#) and [Appendix B](#). Suspected irAEs should be discussed with the medical monitor when possible.

8.9. Product Complaints

The sponsor collects product complaints on study drugs and drug delivery systems used in clinical studies in order to ensure the safety of study participants, monitor quality, and facilitate process and product improvements.

All product complaints associated with material packaged, labeled, and released by the sponsor or its designee will be reported to the sponsor. All product complaints associated with other study material will be reported directly to the respective manufacturer.

The investigator or his/her designee is responsible for reporting a complete description of the product complaint via email or other written communication to the sponsor contact or respective manufacturer as noted in the packaging information. Any AE associated with a product complaint should be reported as described in [Section 8.1.2](#) of this Protocol.

If the investigator is asked to return the product for investigation, he/she will return a copy of the product complaint communication with the product.

9. STATISTICS

9.1. Study Populations

The full analysis set includes all subjects enrolled in the study who received at least 1 dose of study drug (INCAGN01876). This population will be used in the analyses of demographic, baseline, safety, study drug administration, and efficacy data.

The PK evaluable population includes subjects who received at least 1 dose of study drug and had at least 1 postdose PK sample collected and analyzed.

[REDACTED]

[REDACTED]

9.2. Selection of Sample Size

9.2.1. Sample Size for Part 1

The primary objective of Part 1 of the study is to determine the MTD or PAD and DLT of INCAGN01876. The total number of subjects will depend on the number of dose levels tested before the MTD or PAD is established. Approximately 48 subjects (6 subjects per dose level for 8 dose levels) will be included based on the dose escalation. Dose escalation will follow the 3 + 3 design algorithm. Based on this algorithm, a minimum of 3 evaluable subjects will be enrolled in each cohort with a maximum of 6 evaluable subjects in each cohort. The probabilities of dose escalation from a given dose level for the various DLT rates are provided in [Table 15](#).

Table 15: Probability of Dose Escalation for Various DLT Rates

True DLT Rate	Probability of Dose Escalation
20%	70.9%
30%	49.4%
40%	30.9%
50%	17.2%
60%	8.2%

For example, if the true DLT rate is 50% at a given dose level, there is a 17.2% chance that the dose would be escalated. Further, if the true DLT rate is 20%, there is a 70.9% chance that the dose would be escalated. If the MTD is not determined at the highest dose level tested during the study, then the MTD is at or above the highest dose level. The MTD is below the lowest dose level of INCAGN01876 if the Cohort 1 dose is not well tolerated. The PAD may be used in lieu of the MTD and/or prescribed doses may need to be altered in order to determine the MTD.

Part 1 of the study may also include safety expansion cohorts evaluating doses and schedules equivalent to or lower than the highest dose levels determined to be safe and/or doses determined to be pharmacologically active. Each safety expansion cohort will enroll 9 evaluable subjects (up to 36 subjects). If < 3 of 9 evaluable subjects experience a DLT, the cohort will be deemed safe. If more than 1 safety expansion cohort is deemed safe, then the RP2D will be determined in conjunction with the investigators and sponsor based on all available safety, PK, [REDACTED] results.

9.2.2. Sample Size for Part 2

Part 2 of the study will further evaluate the safety, tolerability, preliminary efficacy, PK, and pharmacologic activity of the recommended dose of INCAGN01876. The sample size for each tumor type will be guided by the Simon 2-stage design. Let $P_0 = 5\%$ denote a clinically insignificant response rate for all tumor types. In order to determine whether the target response rate (25%) is likely, an initial number of evaluable subjects (9 subjects) treated at the MTD or

PAD and schedule of INCAGN01876 will be enrolled in a cohort (Stage 1). If there is no response for the cohort, it will be concluded that the true response rate is unlikely to be greater than or equal to the target rate, and no more subjects will be enrolled in that tumor type in Stage 2.

In the tumor types in which at least 1 response among the Stage 1 subjects is observed, 8 additional evaluable subjects will be treated in Stage 2 to estimate the response rate. At the end of Stage 2, if ≤ 2 subjects have responded among the evaluable subjects, the drug will be declared nonpromising for that tumor type. In other words, after the study is finished, if there is a sufficient number of responses in the 2 stages combined, the study compound is considered promising; otherwise it is considered nonpromising. The detailed calculation is based on a 1-sided Type I error of 0.05 and power of 80% for each of the tumor types.

9.3. Level of Significance

For the primary efficacy endpoints, the 1-sided Type I error will be controlled at 0.05 for each individual cohort expansion. Note that this level of significance does not account for the multiple expansion cohorts. For other endpoints, confidence intervals will be reported at a 95% confidence level.

9.4. Statistical Analyses

9.4.1. Efficacy Analyses

9.4.1.1. Primary Efficacy Analyses

In Part 2, the proportion of subjects who meet the objective response criteria (CR + PR) per mRECIST v1.1 will be summarized by tumor type.

If there are no responses in each tumor type out of 9 evaluable subjects (consistent with a calculated response rate $< 5\%$) at Stage 1, then the study will be stopped for futility, and the null hypothesis is not rejected. Otherwise, in the tumor types in which at least 1 response among the evaluable Stage 1 subjects is observed, 8 additional evaluable subjects will be treated in Stage 2. If there are ≤ 2 responders among the evaluable subjects at the end of Stage 2, then the drug will be declared nonpromising for that tumor type, and the null hypothesis is not rejected. Further investigation of the study drug will be considered interesting (predictive of $\geq 25\%$ response rate) if ≥ 3 responses are observed in the first 17 evaluable subjects. For the hypothesis test in the Simon 2-stage design, the null response rate is 5% and alternative response rate is 25%.

9.4.1.2. Secondary Efficacy Analyses

The PK of INCAGN01876 will be summarized.

Duration of disease control, defined as the proportion of subjects who have disease control (CR + PR + SD), as per RECIST v1.1 and mRECIST v1.1 until the earliest date of disease progression will be summarized.

Progression-free survival and duration of response will be estimated using the Kaplan-Meier method as per RECIST v1.1 and mRECIST v1.1.

[REDACTED]

9.4.2. Safety Analyses

9.4.2.1. Adverse Events

A treatment-emergent AE is any AE either reported for the first time or worsening of a pre-existing event after the first dose of study drug. Analysis of AEs will be limited to treatment-emergent AEs, but data listings will include all AEs regardless of their timing to study drug administration. Adverse events will be tabulated by the MedDRA preferred term and system organ class. Severity of AEs will be based on the NCI CTCAE v4.03 using Grades 1 through 4.

The subset of AEs considered by the investigator to have a relationship to study drug will be considered to be treatment-related AEs. If the investigator does not specify the relationship of the AE to study drug, then the AE will be considered treatment-related. The incidence, frequency, duration, and severity of AEs and treatment-related AEs will be tabulated.

9.4.2.2. Clinical Laboratory Tests

Laboratory test values outside of the normal range will be assessed for severity based on the normal ranges for the clinical reference laboratory. The incidence of abnormal laboratory values and shift tables relative to baseline will be tabulated.

Laboratory data will be classified into Grades 1 through 4 using CTCAE v4.03. The following summaries will be produced for the laboratory data:

- Number and percentage of subjects with worst postbaseline CTCAE grade (regardless of baseline value). Each subject will be counted only for the worst grade observed postbaseline.
- Shift tables from baseline to the worst postbaseline value using CTCAE grade.
- For laboratory parameters where CTCAE grades are not defined, shift tables to the worst postbaseline value using the low/normal/high classifications based on laboratory reference ranges.

9.4.2.3. Vital Signs

Descriptive statistics and mean change from baseline will be determined for vital signs (blood pressure, pulse, respiratory rate, and body temperature) at each assessment time. Vital sign results will be reviewed for clinically notable abnormalities (see Table 16), and subjects exhibiting clinically notable vital sign abnormalities will be listed. A value will be considered an "alert" value if it is outside the established range and shows a > 25% change from baseline.

Table 16: Criteria for Clinically Notable Vital Sign Abnormalities

Parameter	High Threshold	Low Threshold
Systolic blood pressure	> 155 mmHg	< 85 mmHg
Diastolic blood pressure	> 100 mmHg	< 40 mmHg
Pulse	> 100 bpm	< 45 bpm
Temperature	> 38°C	< 35.5°C
Respiratory rate	> 24/min	< 8/min

9.4.2.4. Electrocardiograms

Descriptive statistics and mean change from baseline will be determined for each ECG parameter at each assessment time. Electrocardiogram results will be reviewed for clinically notable abnormalities according to predefined criteria (Table 17). Subjects exhibiting clinically notable ECG abnormalities will be listed.

Table 17: Criteria for Clinically Notable Electrocardiogram Abnormalities

Parameter	High Threshold	Low Threshold
QTcF	> 460 msec	< 295 msec
PR	> 220 msec	< 75 msec
QRS	> 120 msec	< 50 msec
QT	> 500 msec	< 300 msec
RR	> 1330 msec	< 600 msec

QTcF = Fridericia correction.

9.4.3. Pharmacokinetic Analysis

The PK parameters of C_{max} , t_{max} , C_{min} , and AUC_{0-t} (INCAGN01876) will be summarized by part, dose, and study cycle. The log-transformed PK parameters will be compared among dose levels by using a 1-factor analysis of variance. Dose-dependent parameters (C_{max} and AUC) will be normalized to the lowest common dose before statistical comparisons. Additionally, if sufficient data are available, then the dose proportionality of INCAGN01876 C_{max} and AUC will be evaluated statistically by using a power model (eg, $AUC = \alpha \cdot (\text{dose})^\beta$) or equivalently $\log(AUC) = \log(\alpha) + \beta \cdot \log(\text{dose})$, where linear dose proportionality is accepted if β is not significantly different from 1). Refer to Appendix C for a detailed list and description of the PK parameters.

If there is a sufficient amount of plasma concentration data from this study, then the data will be analyzed by standard population PK methods using appropriate software (eg, NONMEM).

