2.2.2. Secondary Endpoints

- The PK of INCAGN01876 including C_{max} , t_{max} , C_{min} , and AUC_{0-t} for subjects in Parts 1 and 2 will be summarized.
- Objective response rate, defined as the percentage of subjects having complete response (CR) or partial response (PR), will be determined by investigator assessment of radiographic disease assessments per RECIST v1.1 and mRECIST v1.1.
- Duration of response, defined as the time from earliest date of disease response (CR or PR) until earliest date of disease progression, will be determined by investigator assessment of radiographic disease assessments per RECIST v1.1 and mRECIST v1.1, or death due to any cause if occurring sooner than progression.
- Duration of disease control (CR, PR, and stable disease [SD]), as measured from first report of SD or better until disease progression, will be determined by investigator assessment of radiographic disease assessments per RECIST v1.1 and mRECIST v1.1, or death due to any cause, if occurring sooner than progression.
- Progression-free survival, defined as the time from date of first dose of study drug until the earliest date of disease progression, will be determined by investigator assessment of objective radiographic disease assessments per RECIST v1.1 and mRECIST v1.1, or death due to any cause if occurring sooner than progression.

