7.8. Pharmacokinetic Assessments

7.8.1. Blood Sample Collection

Pharmacokinetic [REDACTED] samples will be obtained at the visits indicated in [Table 9](#). Timing of PK [REDACTED] assessments are outlined in [Table 13](#). After the predose PK sample is drawn, subjects will begin the study drug infusion. Predose is defined as within 24 hours before administration of study drug. Adjustments to the timing of blood sampling may be made based on emerging PK data. The exact date and time of each PK blood draw will be recorded in the eCRF. Instructions for sample preparation and shipping will be provided in the Laboratory Manual.

Table 13: Timing of Pharmacokinetic [REDACTED] Sample Collection

Study Visit	Assessment	Timing of Sample Collection
Cycle 1 Day 1	PK [REDACTED]	• Preinfusion
	PK	• Postinfusion (\pm 10 min) • 4 h (\pm 30 min) postinfusion
Cycle 1 Day 2	PK	• 24 h (\pm 60 min) postinfusion
Cycle 1 Day 7	PK	• Untimed PK sample
Cycle 2 Day 1	PK	• Preinfusion
Cycle 3 Day 1	PK [REDACTED]	• Preinfusion
Cycle 4 Day 1	PK	• Preinfusion
Cycle 6 Day 1	PK [REDACTED]	• Preinfusion
	PK	• Postinfusion (\pm 10 min) • 4 h (\pm 30 min) postinfusion
Cycle 6 Day 2	PK	• 24 h (\pm 60 min) postinfusion
Cycle 6 Day 7	PK	• Untimed PK sample
Cycle 7 Day 1	PK	• Preinfusion
[REDACTED]	[REDACTED]	[REDACTED]

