APPENDIX C. PHARMACOKINETIC ANALYTICAL PARAMETERS

C_{ave}	Average steady-state plasma concentration ($AUC_{0-12h}/12h$ or $AUC_{0-24h}/24h$)
C_{max}	Maximum observed plasma concentration
C_{min}	Minimum observed plasma concentration during the dosing interval
T_{max}	Time to maximum plasma concentration
AUC_{0-t}	Area under the single-dose plasma concentration-time curve from Hour 0 to the last quantifiable measurable plasma concentration, calculated by the linear trapezoidal rule for increasing concentrations and the log trapezoidal rule for decreasing concentrations
$AUC_{0-\tau}$ (ie, AUC_{0-12h} or AUC_{0-24h})	Area under the steady-state plasma concentration-time curve over 1 dosing interval (ie, from Hour 0 to 12 for BID administration or from Hour 0 to 24 for QD administration), calculated by the linear trapezoidal rule for increasing concentrations and the log trapezoidal rule for decreasing concentrations
λ_z	Apparent terminal phase disposition rate constant, where λ_z is the magnitude of the slope of the linear regression of the log concentration versus time profile during the terminal phase
$t_{1/2}$	Apparent plasma terminal phase disposition half-life (whenever possible), where $t_{1/2} = (\ln 2) / \lambda_z$
Cl/F	Oral dose clearance
V_z/F	Apparent oral dose volume of distribution
Fluctuation	Steady-state fluctuation ($(C_{max} - C_{min})/C_{ave}$)

In addition, the following PK parameters may be calculated, whenever possible, for each subject:

A_e	Amount of drug excreted in the urine over sampling interval
Cl_r	Renal clearance, where $Cl_r = A_e/AUC$
% Excreted or f_e	percent excreted in the urine, where % Excreted = $100 (A_e/\text{dose})$

Pharmacokinetic calculations will be performed, if appropriate, using commercial software such as WinNonlin[®] (Pharsight Corporation, Cary, NC). Additional details of analyses will be described in the statistical analysis plan.

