# LIST OF ABBREVIATIONS

| Abbreviation         | Term  |  |
|----------------------|---|--|
|                      |   |  |
| AE                   | adverse event   |  |
| AUC                  | area under the concentration-time curve   |  |
| AUC (0-t) | AUC from time zero (predose) to time of last observed quantifiable concentration within a subject across all treatments |  |
| CI                   | confidence interval   |  |
| $C_{max}$            | maximum observed concentration  |  |
| $C_{min}$            | minimum observed concentration  |  |
| CR                   | complete response   |  |
| CRF                  | case report form  |  |
| CSR                  | Clinical Study Report   |  |
| CTCAE                | Common Terminology Criteria for Adverse Events  |  |
| CTEP                 | Cancer Therapy Evaluation Program   |  |
| DLT                  | dose-limiting toxicity  |  |
| DOR                  | duration of response  |  |
| ECG                  | electrocardiogram   |  |
| ECOG                 | Eastern Cooperative Oncology Group  |  |
| EOS                  | end of study  |  |
| ЕОТ                  | end of treatment  |  |
| FAS                  | full analysis set   |  |
| FDA                  | Food and Drug Administration  |  |
|                      |   |  |
| irAE                 | immune-related adverse event  |  |
| JTc                  | corrected JT interval   |  |
| KM                   | Kaplan-Meier  |  |
| MedDRA               | Medical Dictionary for Regulatory Activities  |  |
| MNTD                 | maximum number of tolerated doses   |  |
| mRECIST              | modified Response Evaluation Criteria in Solid Tumors   |  |
| MSI                  | microsatellite instability  |  |
| MSKCC                | Memorial Sloan Kettering Cancer Center  |  |
| MTD                  | maximum tolerated dose  |  |
| NE                   | not evaluable   |  |
| NSCLC                | non-small cell lung cancer  |  |
| ORR                  | objective response rate   |  |

| Abbreviation     | Term   |  |
|------------------|--|--|
| PAD              | pharmacologically active dose  |  |
| PD               | progressive disease  |  |
| PD-1             | programmed death-1   |  |
| PD-L1            | programmed death ligand-1  |  |
| PFS              | progression-free survival  |  |
| PK               | pharmacokinetic  |  |
| PP               | per protocol   |  |
| PR               | partial response   |  |

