## 7.6. Pharmacokinetic Analyses

The PK calculations will be performed, if appropriate, using commercial software such as WinNonlin® (Pharsight Corporation, Mountain View, CA). Nominal times will be used in all cases, except when the difference between the actual time and nominal time is greater than 5 minutes for samples collected up to 4 hours after administration; in these cases, actual time will be used for PK analysis.

The PK parameters of  $C_{max}$ ,  $t_{max}$ ,  $C_{min}$ , and  $AUC_{0-t}$  (INCAGN01876) will be summarized by part, dose, and study cycle. The log-transformed PK parameters will be compared among dose levels by using a 1-factor analysis of variance. Dose-dependent parameters ( $C_{max}$  and AUC) will be normalized to the lowest common dose before statistical comparisons. Additionally, if sufficient data are available, the dose proportionality of INCAGN01876  $C_{max}$  and AUC will be evaluated statistically by using a power model (eg, AUC =  $\alpha \cdot (dose^{\beta})$ ) or equivalently log (AUC) = log( $\alpha$ ) +  $\beta \cdot log$  (dose), where linear dose proportionality is accepted if  $\beta$  is not significantly different from 1).

If there is a sufficient amount of plasma concentration data from this study, then the data will be analyzed by standard population PK methods using appropriate software (eg, NONMEM). The effect of covariates on PK parameters will be evaluated. The covariates will include, but not be limited to, demographics (age, weight, sex, race), clinical laboratory test values, and concomitant medications.

The relationship between plasma concentrations of INCAGN01876 and the baseline-subtracted change in QTc interval will be explored graphically and analyzed using a linear mixed-effect model.

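### The dose-level ANOVA takes in Cmin without dose normalisation, so its Cmin result does not bear on dose proportionality (minor)

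*Protocol*

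**What the plan says.** Protocol 9.4.3 lists four parameters (Cmax, tmax, Cmin, AUC0-t), which "will be summarized by part, dose, and study cycle". The next sentence reads: "The log-transformed PK parameters will be compared among dose levels by using a 1-factor analysis of variance". No parameter is excluded. The sentence after that puts Cmax and AUC in brackets as the dose-dependent parameters, and these "will be normalized to the lowest common dose before statistical comparisons". SAP 7.6 repeats the rule unchanged. The power model that follows in both documents also covers only Cmax and AUC.

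Protocol Appendix C defines Cmin as "Minimum observed plasma concentration during the dosing interval". The SAP's abbreviation list has only "minimum observed concentration". Table 13 in Protocol 7.8.1 draws a preinfusion PK sample on Cycle 1 Day 1 and further preinfusion samples on Day 1 of Cycles 2, 3, 4, 6 and 7. I found no rule in either document for a Cmin that is zero or below quantification.

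**The concern.** Trough concentration rises with dose, as Cmax and AUC do. Comparing it among dose levels without dividing by dose tests whether troughs are the same at 0.03 mg/kg as at 20 mg/kg. The answer is known in advance, and it is not the question that normalising Cmax and AUC is meant to answer, namely whether exposure departs from proportionality. Cmin is a named secondary PK parameter, and neither the ANOVA as written nor the power model examines its proportionality. A very small p-value for Cmin in the study report could be mistaken for a finding about the kinetics.

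**Working it through.** The documents give no power, alpha or variability for this ANOVA, so there is no stated figure to reproduce.

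**Inputs**
- Doses: 0.03, 0.1, 0.3, 1, 3, 5, 10 and 20 mg/kg (Protocol Table 2, without Cohort -1). The SAP's Table 1 stops at 10 mg/kg. The ranges are 20/0.03 = 667-fold and 10/0.03 = 333-fold.
- Subjects per level: n = 3 to 6 (Protocol 9.2.1).
- Reference case: Cmin exactly proportional to dose. Protocol 1.2.1 reports dose-independent clearance, half-life and volume in monkeys, so this is a fair reference.
- Assumed: two-sided alpha 0.05, in line with the 95% confidence level in Protocol 9.3, and between-subject CV of 30% to 150%.

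**Method**

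Under proportionality the mean of log Cmin at dose d is ln(d) plus a constant. With k levels, n per level and σ² = ln(1 + CV²):
- S = Σ(ln d − mean ln d)²
- noncentrality λ = n × S / σ²
- P(reject) = P(noncentral F with k − 1 and k(n − 1) degrees of freedom and noncentrality λ exceeds the 95% point of central F)

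S is 37.00 for the eight protocol doses and 27.57 for the SAP's seven. For 5, 10 and 20 mg/kg it is 2 × (ln 2)² = 0.961.

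At CV 150%, σ² = ln(3.25) = 1.179. With n = 3:
- Eight doses: λ = 3 × 37.00 / 1.179 = 94.2, critical F(7, 16) = 2.66
- Seven doses: λ = 3 × 27.57 / 1.179 = 70.2, critical F(6, 14) = 2.85
- 5, 10, 20 mg/kg: λ = 3 × 0.961 / 1.179 = 2.4, critical F(2, 6) = 5.14

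**P(reject), un-normalised Cmin, exactly proportional PK**

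| Doses (mg/kg) | n | CV 30% | CV 50% | CV 100% | CV 150% |
|---|---|---|---|---|---|
| 0.03 to 20 (8 levels) | 3 | 1.000 | 1.000 | 1.000 | 1.000 |
| 0.03 to 20 (8 levels) | 6 | 1.000 | 1.000 | 1.000 | 1.000 |
| 0.03 to 10 (7 levels) | 3 | 1.000 | 1.000 | 1.000 | 0.9998 |
| 0.03 to 10 (7 levels) | 6 | 1.000 | 1.000 | 1.000 | 1.000 |
| 5, 10, 20 | 3 | 0.979 | 0.693 | 0.277 | 0.179 |
| 5, 10, 20 | 6 | 1.000 | 0.988 | 0.641 | 0.416 |

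For 1, 3 and 10 mg/kg at n = 3 the probability is 0.985, 0.788 and 0.53 at CV 50%, 80% and 120%.

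**With normalisation**

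Dividing Cmin by dose removes ln(d) from every mean, so λ = 0 and the rejection rate is the nominal 5%. Simulation over the eight doses (4,000 runs per setting, n = 3 or 6, CV 30% to 150%) gave 4.5% to 5.6%.

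**The case against.** The best defence is that little rests on this test. The secondary endpoint is that the PK parameters "for subjects in Parts 1 and 2 will be summarized". SAP 3.3 calls all analyses exploratory, and the recommended dose is to be chosen on all available safety and PK results (Protocol 9.2.1, SAP 3.1.2), with no rule that uses an ANOVA p-value. The same section already gives a normalised ANOVA and a power model for Cmax and AUC, and population PK if the data suffice. All of this stands, and it keeps the point minor. It does not make the Cmin comparison informative.

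Four stronger readings are tempting, and the documents do not support them.

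- *The plan cannot tell linear from nonlinear PK.* The Cmax and AUC analyses address that. The gap is confined to Cmin.
- *Rejection is a foregone conclusion.* That is fair over the full dose range. Over narrow or noisy sets it is not, as the 5, 10 and 20 mg/kg rows show. An omnibus F also gives no direction, so a significant result would not by itself show that larger doses give larger troughs.
- *Cycle 1 Cmin will be zero and cannot be logged.* Appendix C limits Cmin to the dosing interval, and Protocol 7.8.1 says "After the predose PK sample is drawn, subjects will begin the study drug infusion". The Cycle 1 Day 1 predose sample can therefore be read as falling before the first interval. On the other side, the SAP entry has no time limit and its AUC definition takes predose as time zero: "AUC from time zero (predose) to time of last observed quantifiable concentration". The text leaves the matter unsettled, which is a reason to clarify it and not proof of an error.
- *tmax can take only two values, so its ANOVA is invalid.* Protocol 7.8.2 uses actual times when a sample up to 4 hours deviates by more than 5 minutes, Table 13 allows windows of 10 and 30 minutes, and there are 24-hour and Day 7 samples. Values will cluster at a few times, which makes median and range the better summary, but no more than that. Leaving tmax un-normalised is not a fault, since it is not expected to scale with dose.

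**Conclusion.** The point holds for Cmin. As both documents are written, Cmin is tested among dose levels on its raw scale, and the result says nothing about dose proportionality. Under proportional PK, rejection is all but certain over either document's full dose range, and above the nominal 5% in every narrower set examined.

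The figures rest on an assumed alpha and CV, on exact proportionality, and on every included level giving measurable troughs. No assay limit is stated, so if the lowest doses fall below quantification, the narrower sets are the relevant ones.

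Severity is minor. This is a wording gap in an exploratory analysis of a secondary endpoint that feeds no decision rule.

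**What to change.** In Protocol 9.4.3 and SAP 7.6, extend the bracketed list to Cmax, Cmin and AUC, or take Cmin out of the ANOVA. If Cmin stays in, run the comparison within one dosing interval only (14, 21 or 28 days), because dividing by dose does not make troughs from different intervals comparable.

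For clarity, define Cmin per cycle as the preinfusion concentration at the end of that interval: the Cycle 2 Day 1 sample for Cycle 1 and the Cycle 7 Day 1 sample for Cycle 6. State that the Cycle 1 Day 1 predose sample is excluded, and give a rule for troughs below quantification, which are likeliest at the low doses.

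As a secondary suggestion, report tmax as median and range and not by log-scale ANOVA.

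The cost is a few sentences in each document and some reprogramming. No new samples or visits are needed. Splitting by interval will leave fewer subjects per comparison if more than one schedule is used.
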